2.2 SECONDARY OBJECTIVES AND ENDPOINTS

Secondary objectives of the study include determining whether as needed PCP follow-up, compared to scheduled PCP follow-up:

- Does not adversely impact satisfaction with care?
- Does not adversely impact the relationship between the child's primary caregiver and the child's PCP?
- Does not prolong time to resolution of symptoms?
- Does not increase risk of hospital re-admissions and emergency department visits?
- Results in a fewer number of post-discharge ambulatory visits?
- Results in less ambulatory testing (pulse oximetry, chest x-ray) and fewer prescriptions (albuterol, antibiotics, steroids)?
- Results in fewer missed days from daycare and work?
- Results in lower medical costs?

Secondary Outcomes

Measured by parent report via weekly research coordinator phone calls, until symptoms resolved or 50 days after discharge, whichever occurs first:

- Time from hospital discharge to cough resolution
- Time from hospital discharge to child reported back to normal

Measured by parent report via weekly research coordinator phone calls, until symptoms resolved or 50 days after discharge, whichever occurs first:

- Number of hospital re-admissions and emergency visits
- Number of ambulatory visits
- Number of missed daycare and work days
- Ambulatory prescriptions (albuterol, antibiotics, steroids)
- Ambulatory testing (i.e. pulse oximetry, chest x-ray)- only measured at first ambulatory visit

Measured by parent report via research coordinator phone call at 1 month from discharge:

- Relationship with PCP measured by the Patient-Doctor Depth-of-Relationship Scale²⁴
- Satisfaction with care, measured by applicable questions from the Patient Satisfaction Questionnaire Short Form (PSQ-18)²⁵
- Immunizations received

Measured among patients cared for at Intermountain clinics and those who have Select Health insurance:

- Total charges for ambulatory medical care from discharge until:
 - 14 days after discharge
 - symptom resolution

Measured at the time of discharge and during the first follow up phone call:

• Perceptions about pulse oximetry monitoring

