7.2 STATISTICAL ANALYSES

7.2.1 ANALYSIS OF THE PRIMARY AND SECONDARY ENDPOINT(S)

Intent-to-treat analysis for primary outcome

The primary non-inferiority analysis will be an analysis of covariance comparing HADS scores approximately 7 days after discharge between patients randomized to scheduled PCP follow up or as needed PCP follow up, controlling for baseline HADS scores. A 1-sided upper 97.5% confidence bound for the difference in mean HADS score between the intervention and control groups will be constructed, and non-inferiority will be inferred if the upper confidence limit excludes the intent-to-treat non-inferiority (ITT) bound of 1.08 points.

ITT comparisons for secondary outcomes

A log-rank test will be used to compare the time from discharge to the first report of symptom resolution between the randomized treatment groups. Follow-up for symptom resolution will be right-censored at 50 days after discharge or at the time of loss-to-follow-up. Charges will be compared between the two intervention groups using two-part models, given that charge data will likely be semi-continuous. Other secondary outcomes will be compared between the randomized groups using Poisson or negative binomial models with robust standard errors for statistical inference.

Instrumental variable analysis of the effect of the routine follow-up visit

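### The count-model rule in Section 7.2.1 also covers the PCP-relationship and satisfaction scores, so under the usual log link their effect is a ratio that depends on how the scale is scored

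*Combined protocol and SAP*

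**What the plan says.** Section 7.2.1 analyses the primary outcome, a HADS anxiety score, by analysis of covariance and judges it on a difference in mean points. Two groups of secondary outcomes get their own method:

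- Symptom resolution: "A log-rank test will be used to compare the time from discharge to the first report of symptom resolution between the randomized treatment groups".
- Charges: "Charges will be compared between the two intervention groups using two-part models".

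Everything else falls under one sentence: "Other secondary outcomes will be compared between the randomized groups using Poisson or negative binomial models with robust standard errors for statistical inference". It makes no exception and states no link function, covariates or reporting scale.

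Section 2.2 lists three questionnaire-type outcomes among those left over:

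- "Relationship with PCP measured by the Patient-Doctor Depth-of-Relationship Scale", at one month.
- "Satisfaction with care, measured by applicable questions from the Patient Satisfaction Questionnaire Short Form (PSQ-18)", also at one month. The items and their scoring are not given.
- "Perceptions about pulse oximetry monitoring", with the timing "Measured at the time of discharge and during the first follow up phone call". The response format is not given.

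Two of the eight secondary objectives in Section 2.2 ask whether as needed follow-up harms satisfaction or the caregiver's relationship with the PCP.

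**The concern.** Poisson and negative binomial models describe counts, and with the usual log link they report a ratio of means. That suits visits or missed days, where zero means none. A questionnaire score has no such zero. Whether an item runs 0–4 or 1–5, and which end is favourable, is a convention, and the ratio changes with it. Since the plan does not give the scoring, the size of the reported effect is not fixed in advance.

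This matters because both objectives are about absence of harm. To answer them, a reader must judge how large a worsening the data still allow, so the effect estimate and its interval count for more than the p-value. A percentage ratio that moves with the scoring is hard to use for that.

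A smaller, related gap is that perceptions of pulse oximetry are collected twice, and the plan gives the discharge value no stated role.

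**Working it through.** **The plan's own figure.** The only sample-size figure is for the primary outcome (Section 7.1).
- Margin: 2 × (1 − 0.33 − 0.13) = 1.08.
- Residual SD: 4.1 × √(1 − 0.65²) = 3.116.
- Per arm: 2 × (1.960 + 0.842)² × 3.116² / 1.08² gives 131 after rounding up. Dividing by 0.90 gives 146, so 292 in total against the stated 294.

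The figure reproduces, and nothing below touches it. No precision target is stated for the secondary scores.

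**Step 1: match outcomes (Section 2.2) to methods (Section 7.2.1).**

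| Outcome | Type | Method stated | Suitable? |
|---|---|---|---|
| Cough resolution, back to normal | time to event | log-rank | not at issue |
| Charges | semi-continuous | two-part model | not at issue |
| Re-admissions, emergency and ambulatory visits, missed days, prescriptions | counts | Poisson / negative binomial | yes |
| Tests at first visit, immunizations | yes/no, as I read them | same rule | yes; robust Poisson gives a risk ratio |
| PCP relationship, satisfaction | questionnaire scores | same rule | poor effect measure |
| Pulse-oximetry perceptions | format not given | same rule | cannot be judged |

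**Step 2: effect of scoring on one item.** The documents give no scoring, so assume a five-point item with means of 3.6 (as needed) and 4.0 (scheduled) on 1–5.
- Scored 1–5: 3.6 / 4.0 = 0.90.
- Scored 0–4: 2.6 / 3.0 = 0.87.
- 1–5 reversed: (6 − 3.6) / (6 − 4.0) = 2.4 / 2.0 = 1.20.

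The difference is 0.4 points in size each time. The same answers read as 10% lower, 13% lower or 20% higher. The reversed ratio is not even the reciprocal of the first (1 / 0.90 = 1.11).

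**Step 3: effect of scoring on a sum score.** Assume eight items and a 2-point difference.
- Items 0–4: 22 / 20 = 1.10; reversed, 10 / 12 = 0.83.
- Items 1–5: 30 / 28 = 1.07; reversed, 18 / 20 = 0.90.

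**Step 4: one simulated data set scored four ways.** Assumptions: 132 per arm (147 × 0.90), SD 7 before rounding and truncation to 0–32, Poisson with log link and robust standard errors.

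| Scoring | Ratio (95% CI) | Size of mean difference |
|---|---|---|
| 0–32 | 1.067 (0.993 to 1.148) | 1.31 |
| 8–40 | 1.048 (0.995 to 1.104) | 1.31 |
| 0–32 reversed | 0.896 (0.793 to 1.012) | 1.31 |
| 8–40 reversed | 0.936 (0.870 to 1.007) | 1.31 |

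The p-value for the ratio was 0.077 to 0.078 under every scoring, and 0.078 for the mean difference. On the 0–32 and 8–40 scorings the mean difference has a 95% CI of −0.15 to 2.77; reversal only changes its sign.

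**Step 5: validity of the test.** In 5,000 simulated null trials under the same assumptions, the two-sided 5% test rejected in 5.1% with robust Poisson and 5.2% with the difference in means.

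**Step 6: what a discharge perception value could add.** If it is a pre-randomization rating with correlation r to the first-call value, adjustment multiplies the standard error by √(1 − r²). This is 0.954 at r = 0.3, 0.866 at 0.5 and 0.760 at 0.65, a reduction of 5%, 13% and 24%. These correlations are assumed; 0.65 is the plan's value for HADS, not for perceptions.

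**The case against.** The strongest reply is that nothing of substance is lost. Robust standard errors keep the test valid, and p-values hardly move with the scoring. With treatment as the only regressor, the Poisson fitted means are exactly the arm means, so the difference in points and essentially the same interval can be recovered from the plan's own model. Section 7.2.1 states no link and does not say that only a ratio will be reported. The mean difference would not settle the two objectives by itself either, because no margin is set for them.

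Much of this stands. It limits the point to the effect measure and removes any claim about false positives. It does not remove the point. The plan names a count model for scores that are not counts. That model's usual output is a ratio, and nothing commits the analysts to converting it to points or fixes the scoring. HADS, also a questionnaire score, is already analysed as a difference in mean points in the same section.

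Three stronger readings are tempting but not supported:

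- **That the negative binomial fit would fail on ratings.** Convergence depends on the optimizer and on whether single items or sums are modelled. The plan equally allows Poisson.
- **That the discharge perception value goes unused.** The plan is silent on its use. It could be an outcome in its own right.
- **That this value is a ready baseline covariate.** Section 6.2 names only the HADS as a questionnaire completed before randomization. Randomization takes place on the day of discharge, and families are then told their assignment. Perceptions at discharge may come before or after that, and their format may not be a rating.

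**Conclusion.** The point holds for the relationship and satisfaction scores. Section 7.2.1 literally sends them to count models, and no other section exempts them. Under the usual log link, the same answers can read as a ratio of 0.90, 0.87 or 1.20 (assumed five-point item) while the difference stays at 0.4 points. The sizes rest on assumed scorings and on the log link as the default, because the documents state neither. The dependence on origin and direction is a property of any ratio of means and needs no such assumption.

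A reader might infer an inflated error rate or a secondary conclusion that would flip; the calculations show neither. What suffers is the ability to read how much harm the data still allow. For perceptions, the supported statement is narrower: no use of the discharge value is specified, and its timing relative to randomization and its format are not documented. The change is worth making before analysis. The primary analysis and the sample size of 294 are unaffected.

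**What to change.** In Section 7.2.1, replace the single residual rule with three:

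1. **Counts** (re-admissions and emergency visits, ambulatory visits, missed days, prescriptions): Poisson or negative binomial models with robust standard errors, as now.
2. **Yes/no items** (tests at the first ambulatory visit, immunizations): robust Poisson, reporting risk ratios.
3. **Relationship and satisfaction scores**: linear regression with robust standard errors, reporting the mean difference in scale points with a 95% CI. State which PSQ-18 items are used, and give the range and direction of each score.

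For pulse-oximetry perceptions, state the response format and when the discharge value is taken relative to randomization. If it is a rating and confirmed to be collected before randomization, adjust the first-call value for it, in the same form as the HADS analysis. Otherwise do not use it as a covariate.

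Section 7.2.2 refers back to the same tests, so any questionnaire score compared there should follow the new wording.

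The cost is SAP wording, plus a check of the data-collection scripts for the timing and format of the perception question. No patients, visits or measurements are added.

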7.2.2 ANALYSIS OF CHILDREN DISCHARGED HOME WITH SUPPLEMENTAL OXYGEN

All of the same outcomes discussed above will be measured among the subpopulation of un-randomized children discharged home with supplemental oxygen. We will describe parental anxiety and resource utilization among this subpopulation and compare them to patients who are not discharged home on oxygen, using the same statistical tests used for the main analysis.

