6.2 STUDY PROCEDURES

Consent, screening and study enrollment will occur while the participant is hospitalized for bronchiolitis. Eligibility confirmation will be obtained from the electronic medical record along with parent interview as applicable. Prior to randomizing the eligible patient, the child's parent will be asked to complete the anxiety portion of the HADS, administered verbally by research coordinators. When a RedCap enrollment checklist has been completed, RedCap will supply the local research coordinator with the patient's randomization assignment. The parents will be notified of their randomization group and instructed on the study plan for follow-up as discussed in section 6.1. Patients discharged home with supplemental oxygen will not be randomized, with follow up plans determined by the child's medical team.

Prior to hospital discharge, a research coordinator will call the child's PCP to notify them of the child's enrollment in the trial and their randomization assignment. The research coordinator will fax a one page summary of the trial to the PCP. PCPs will be notified at the time of the call and in the one-page summary that the protocol allows for and encourages PCPs to check-in over the phone with families enrolled in the trial.

Demographic and hospitalization details will be obtained via electronic medical record review. Data for the primary endpoint will be collected by administering the anxiety portion of the HADS survey prior to randomization and at the first post discharge follow-up phone call (5-9 days after discharge). Data for the secondary endpoints will be collected via phone calls from a research coordinator and will occur weekly until symptom resolution or 50 days after discharge, whichever comes first. Research

coordinators will follow a script for all data collection phone calls. Electronic medical record review will supplement information collected by phone calls for patients who re-visit the emergency department or are re-admitted to the hospital. In addition, a one month post discharge phone call will be made to administer the Patient-Doctor Depth-of-Relationship Scale questionnaire. Study participation will conclude with the final discharge phone follow up call.

Table 1: Schema of study procedures

Screening/Enrollment Within 2 days of anticipated hospital discharge

- •Screen potential participants by inclusion and exclusion criteria
- •Obtain informed consent and enroll

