6.3 MEASURES TO MINIMIZE BIAS: RANDOMIZATION AND BLINDING

Randomization

After consent and enrollment, a research coordinator at the site will obtain a site-specific computergenerated randomization assignment for each patient. Patients will be randomized with equal (1:1) allocation to either the scheduled PCP follow up group or to the as-needed PCP follow up group, using randomly permuted blocks of random sizes. Randomization sequences will be stratified by site but not by any additional baseline factors. The research coordinator will inform the patient's family, inpatient medical team, and PCP of the patient's assignment.

Blinding

BeneFIT will be an unblinded trial because it will not be feasible to blind parents or research coordinators to intervention assignment, as the reason for any follow-up visit (i.e. routine vs new concern) that occurs needs to be documented. However, investigators responsible for analyses will be blinded to individual patient intervention assignments.

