7 STATISTICAL METHODS

7.1 SAMPLE SIZE DETERMINATION

A previous bronchiolitis trial of 615 patients¹⁹ found a standard deviation for HADS scores of 4.1 and a serial correlation of the HADS score between an admission and 7-day assessment that exceeded 0.80 ([name], personal communication, October 18, 2017). To provide as conservative assessment of statistical power, we assume that the serial correlation over 7 days will equal or exceed 0.65 in the present study. We designated a non-inferiority margin on the anxiety portion of the HADS of 2 points, the smallest clinically meaningful change. Based on the non-adherence to recommended follow-up encountered in our pilot study,²² we estimated that up to 33% of patients randomized to as needed follow up would still follow up and that 13% of patients randomized to scheduled follow up would not attend follow up appointments. Hence, the non-inferiority margin for the ITT analysis of all randomized patients was adjusted to be $2 \times (1-0.33-0.13) = 1.08$. We also assumed that the follow-up anxiety assessment would be obtained for at least 90% of subjects. Under these assumptions, a total sample size of 294 patients (147 patients in each group) will provide 80% power with 1-sided α =0.025 for the analysis of covariance planned for the primary analysis to demonstrate non-inferiority of as needed follow up if in fact as needed follow up and scheduled follow up lead to equal levels of anxiety. Because children discharged home with supplemental oxygen are not being randomized and are not being analyzed in the main analysis, these patients are not included in the power calculation.

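### Section 7.2.2 compares un-randomized oxygen children with patients not on oxygen without site or age adjustment and, read plainly, against both arms pooled, so visit-related results partly reflect the 1:1 allocation

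*Combined protocol and SAP*

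**What the plan says.** All references are to the combined protocol and SAP.

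- **Section 6.2:** "Patients discharged home with supplemental oxygen will not be randomized, with follow up plans determined by the child's medical team". Section 4.3 keeps these children out of the main analyses and promises a separate one.
- **Section 7.2.2:** the same outcomes are measured in these children. Anxiety and resource use are described, and the analysts will then "compare them to patients who are not discharged home on oxygen, using the same statistical tests used for the main analysis". No arm is named as comparator, and no covariate is listed.
- **Section 7.2.1:** the tests being borrowed are defined for the two arms. Anxiety uses ANCOVA with baseline HADS, and charges use two-part models. For the rest, "Other secondary outcomes will be compared between the randomized groups using Poisson or negative binomial models"; the standard errors there are robust. Baseline HADS in the ANCOVA is the only covariate named.
- **Section 6.3:** "Patients will be randomized with equal (1:1) allocation". On stratification: "Randomization sequences will be stratified by site but not by any additional baseline factors".
- **Section 7.1:** for the as-needed arm, planning takes it that "up to 33% of patients randomized to as needed follow up would still follow up". For the scheduled arm, non-attendance is put at 13%.
- **Section 2.2:** the as-needed policy is examined for whether it "Results in a fewer number of post-discharge ambulatory visits", and likewise for less testing, fewer prescriptions and lower costs.

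**The concern.** Two features of the main analysis do not carry over to the oxygen comparison.

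First, randomization is what supports an unadjusted contrast between the arms. It does nothing for oxygen against no oxygen. Oxygen children may be spread differently over the five hospitals and may differ in age, and section 7.2.2 adjusts for neither.

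Second, the patients not on oxygen are not a usual-care group. They are half scheduled and half as needed because the trial made them so, and the plan sets out to show that the two halves differ in visits and in what happens at visits. Oxygen children follow whatever plan their medical team sets. If the arms are pooled, a difference in visits, testing, prescriptions or charges depends in part on the allocation ratio. A pooled difference near zero could be read as similar use when oxygen children differ from both arms in opposite directions.

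**Working it through.** **1. The plan's own figure.** Section 7.2.2 gives no number, so the check starts from section 7.1, which supplies the inputs.
- Margin: 2 × (1 − 0.33 − 0.13) = 1.08.
- Residual SD: 4.1 × √(1 − 0.65²) = 3.116.
- Per arm: 2 × (1.960 + 0.842)² × 3.116² / 1.08², rounded up to 131 evaluable. Then 131 / 0.9 gives 146, or 292 in total against the stated 294.
- Power at 147 × 0.9 = 132.3 evaluable per arm is 80.5%.

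The stated sample size reproduces. Oxygen children do not enter it.

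**2. Attendance in a pooled comparator.** Section 7.1 implies 1 − 0.13 = 0.87 for scheduled and up to 0.33 for as needed.
- At 1:1: 0.5 × 0.87 + 0.5 × 0.33 = 0.60.
- At a hypothetical 2:1 (scheduled to as needed): 0.69. At 1:2: 0.51.

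The 33% is an upper planning value, so 60% is the most the pooled rate would be with 87% in the scheduled arm.

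**3. Gap for oxygen children.** Their attendance is not given, so it is varied. Gap = assumed oxygen attendance − comparator attendance, in percentage points.

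| Oxygen attendance (assumed) | v pooled | v scheduled | v as needed |
|---|---|---|---|
| 33% | -27 | -54 | 0 |
| 50% | -10 | -37 | +17 |
| 60% | 0 | -27 | +27 |
| two-thirds (pilot, section 1.2) | +7 | -20 | +34 |
| 87% | +27 | 0 | +54 |

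For the same oxygen children at two-thirds, 2:1 allocation would give 0.667 − 0.69 = -2 points and 1:2 would give 0.667 − 0.51 = +16, in place of +7.

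**4. What a pooled test would show at two-thirds.** Comparators with data: 294 × 0.9, taken as 264 (132 per arm). For an assumed 30, 50 and 100 oxygen children, the pooled-variance z for +7 points is 0.71, 0.89 and 1.17. None reaches 1.96.

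**5. The listed endpoint.** Section 2.2 counts ambulatory visits rather than attendance at one visit. With k other visits per child in every group (assumed 0, 0.5, 1.0), ratio = (0.667 + k) / (c + k), where c is comparator attendance:
- pooled (c = 0.60): 1.11, 1.06, 1.04
- scheduled (c = 0.87): 0.77, 0.85, 0.89
- as needed (c = 0.33): 2.02, 1.41, 1.25

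The pooled ratio stays near 1 while the arm-specific ratios lie on either side of it.

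**6. Anxiety.** If the arms have equal mean HADS, as section 7.1 assumes for power, pooling shifts nothing.

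**7. Precision cost of separate arms.** With n oxygen children and equal variances, SE ratio = √[(1/n + 1/132) / (1/n + 1/264)]. For n = 30, 50 and 100 this is 1.050, 1.077 and 1.129, so intervals are about 5%, 8% and 13% wider.

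**The case against.** The strongest reply is that section 7.2.2 is a description. It calls the children un-randomized, section 4.3 keeps the analysis separate, and nothing claims an effect of oxygen. For the question of how these families differ from the others, an unadjusted contrast is a legitimate target. ANCOVA, two-part and count models are not invalid because a grouping was not randomized. Section 7.2.1 already compares the arms on the same outcomes, so if group-level values are published a reader could set oxygen children beside each arm.

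Most of this stands, and it keeps the point small. A reader might infer that the tests are wrong for this comparison; the documents do not support that, since the issue is adjustment and choice of comparator. What the reply does not remove is that section 7.2.2 specifies tests as well as description, leaves the comparator unnamed, and does not promise arm-level results beside the oxygen group.

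It is also fair that the illustration rests on assumed inputs. The pilot's two-thirds may not carry over: section 4.2 excludes children whose inpatient team wants PCP follow-up, and if that applies to oxygen children it could lower their attendance.

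**Conclusion.** The point holds as a minor improvement that costs little. As written, the oxygen comparison is unadjusted for site and age. On its plain reading, its visit-related results depend partly on the trial's 1:1 mix of two arms planned to attend at 87% and up to 33%. Pooling is a reading of section 7.2.2, not a statement in it. If pooling is not intended, the comparator still has to be named.

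The +7, -20 and +34 points illustrate one assumed attendance rate. The documents give neither attendance nor numbers for oxygen children, so a reader who infers a bias of known size or direction goes beyond them. A reader might also infer that the trial's main result is compromised. It is not: oxygen children are outside the randomized comparison and the power calculation, so the primary conclusion, the 1.08 margin and N = 294 stand. Anxiety in the oxygen comparison is affected by pooling only if the arms differ.

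**What to change.** In section 7.2.2:

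1. State that the comparator is all randomized children, and report oxygen children against each randomized arm separately as well as overall.
2. Keep baseline HADS in the ANCOVA, and add site and age to the ANCOVA and the count models. Add them to the charge models where the restriction in section 2.2 to Intermountain clinics and Select Health patients leaves enough spread across sites.
3. Give estimates with 95% confidence intervals, labelled observational, and note that confounding by illness severity remains.

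The cost is SAP wording, some extra analysis, and arm-specific intervals about 5%, 8% and 13% wider than pooled ones for an assumed 30, 50 and 100 oxygen children. Site adjustment may widen intervals further, by an amount that depends on how unevenly oxygen children are spread over the five hospitals, which is not given. No extra patients, new data item or change to the randomized analysis is needed.
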